8.4.1 Clinical assessment

- Adverse events
- Concomitant medications
- Transfusion history
- Physical examination including liver and spleen size by palpation, lymph nodes, skin infiltration, gingival hypertrophy,
 cutaneous haemorrhages
- Vital signs and weight

8.4.2 Laboratory assessments

- Full blood count to include haemoglobin, differential white cell count (including monocyte count and blast %), platelet count, MCV
- Biochemistry assessment: sodium, potassium, urea, creatinine (and eGFR), magnesium, calcium, phosphate, glucose,
 albumin, total protein, bilirubin, ALT/AST, alkaline phosphatase, LDH, uric acid

8.4.3 ECG

12-lead electrocardiogram including assessment of QT_c interval (day 1 only of each subsequent cycle, pre-dose)

8.5 Assessment at disease progression or cessation of therapy due to unacceptable toxicity

For patients who stop tefinostat treatment at *time points other than immediately following the post cycle 6 efficacy response* assessment the following additional assessments should be performed. This will include patients in whom tefinostat is

withdrawn early (during cycles 1-5) due to unacceptable toxicity or clear disease progression (including those patients with uncontrolled myelosuppression who require concomitant hydroxycarbamide therapy beyond completion of tefinostat cycle 3 – see section 7.5) and also patients who stop tefinostat treatment due to disease progression or toxicity following a prolonged period of therapy extending beyond cycle 6.

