8.2.10 Quality of life assessment (cycle 4 only)

- Quality of life assessment will be repeated on day 1 of tefinostat cycle 4 (+/- 7 days)
- Patients should complete the EuroQol EQ5D-5L and MPN-SAF questionnaires (see Appendix 9 and 10). Completed
 questionnaires should be returned to CTR using the pre-paid envelopes provided.

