8.3.6 Quality of life questionnaire

- Quality of life assessment will be repeated on day 29 of tefinostat cycle 6 (+/- 7 days)
- Patients should complete the EuroQol EQ5D-5L and MPN-SAF questionnaires (see Appendix 9 and 10).
- Completed questionnaires should be returned promptly to CTR using the pre-paid envelopes provided, or by scan and email (the MPN-SAF Total Symptom Score forms part of the International Consortium MDS/MPN Response Criteria – see appendix 3).

Following this efficacy assessment, a short extension of tefinostat therapy (maximum 14 days) will be permitted in order to allow adequate time for sites to fully assess week 24 response assessment investigations and discuss the results with trial subjects.

'Clinical benefit' from tefinostat will be defined as:

Clinical Benefit (or better) according to International Consortium MDS/MPN Response Criteria (28) in the absence of features of disease progression

(See Appendix 3).

This definition includes 'complete remission', 'complete cytogenetic remission',' partial remission', 'bone marrow responses' or 'clinical benefit' as defined within these criteria.)

Patients who are both benefitting clinically from tefinostat and continuing to tolerate tefinostat therapy will be permitted to continue treatment, pending the availability of study drug, until there is a loss of clinical response, disease progression or the development of unacceptable toxicity. Patients who are not deemed to be obtaining clinical benefit at the time of the end of cycle 6 efficacy assessment will be taken off tefinostat therapy.

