8.5.1 Clinical assessment

- Adverse events
- Concomitant medications
- Transfusion history
- Physical examination including liver and spleen size by palpation, lymph nodes, skin infiltration, gingival hypertrophy,
 cutaneous haemorrhages
- Vital signs and weight
- ECOG performance status (Appendix 6)

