9.2 Quality of Life data collection

CMML has a heterogeneous clinical phenotype with a variable spectrum of disease-related constitutional symptoms. Previous studies of non-selective HDAC inhibitors have been associated with generalised systemic toxicities including gastrointestinal effects, fatigue and insomnia with resulting impacts on quality of life (QoL). QoL is thus an additional important outcome measure in assessing impact of tefinostat treatment in this patient population. QoL will be measured at baseline (prior to the start of treatment) and following 3 and 6 four-week cycles of tefinostat therapy. The instruments used will be the EuroQoL EQ-5D-5L (Appendix 9) and the Myeloproliferative Neoplasm (MPN) Symptom Assessment Form (MPN-SAF) (Appendix 10). The EQ-5D is a standardised instrument for use as a measure of health outcome. The EQ-5D-5L descriptive system comprises five dimensions (mobility, self-care, usual activities, pain/discomfort, anxiety /depression). The

MPN-SAF is a 27-item validated tool which aims to assess the prevalence and severity of symptoms in patients with myeloproliferative neoplasms; its use in patients with myelodysplastic/myeloproliferative neoplasms including CMML is currently being validated. The MPN-SAF Total Symptom Score is currently included within the International Consortium MDS/MPN Response Criteria on an exploratory basis. (28, 29)

Patients should be able to undertake the assessment themselves, and the local trial team are asked to facilitate this and to return the responses promptly to CTR in the pre-paid envelopes.

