10.4 Definition of outcome measures

10.4.1 Primary outcome measures

- Safety and tolerability of tefinostat will be defined as the proportion of patients experiencing a CTC grade 3-4 non-haematological toxicity⁽²⁵⁾ or death during the first two cycles of tefinostatthat is judged by either the principal investigator or the chief investigator (or his delegate) as having a reasonable suspected causal relationship to tefinostat.
- Overall clinical response rate will be defined as the cumulative proportion of patients achieving clinical benefit (or better) according to International Consortium MDS/MPN Response Criteria⁽²⁸⁾ at day 29 of the sixth or last cycle of tefinostat (whichever is the earliest).

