- Neutrophils If pre-treatment neutrophils $\leq 0.5 \times 10^9/I$: increase to $> 0.5 \times 10^9/I$ (and by $\geq 100\%$)
 - If pre-treatment neutrophils 0.5-1.0 x 10^9 /I: an absolute increase of \geq 0.5 x 10^9 /I (and by at least 50%)
- **Spleen** either a minimum 50% reduction in palpable splenomegaly of a spleen that is a least 10cm palpable at baseline or a spleen that is palpable at more than 5cm at baseline becoming not palpable
- **Symptoms** improvement in symptoms as noted by a decrease of ≥50% in the MPN-SAF Total Symptom Score (only valid if baseline score>20)*

Disease Progression (requires a combination of either 2 major, 1 major & 2 minor, or 3 minor criteria from the list below)

Major Criteria of disease progression

Increase in bone marrow blast count: -<5% blasts: ≥50% increase (and to >5% blasts)

- 5-10% blasts: ≥50% increase (and to >10% blasts)

- 10-20% blasts: ≥50% increase (and to >20% blasts)

Evidence of cytogenetic evolution: - appearance of new cytogenetic abnormality

- increase in cytogenetic burden of disease by ≥50%

• New extramedullary disease: - worsening splenomegaly (either from previously inpalpable to

>5cm palpable, or >100% increase in previous 5-10cm

splenomegaly, or ≥50% increase in previous >10cm splenomegaly)

- extramedullary disease outside the spleen (including hepatomegaly, skin lesions, granulocytic sarcoma)

Minor Criteria of disease progression

- New transfusion dependence (at least 2u of red cells in the past month for Hb<85g/l that was not associated with clinically overt bleeding or felt to be associated with therapy
- Significant loss of maximal response of cytopenias: ≥50% decrement from maximum response in neutrophils or platelets (not felt to be associated with therapy)
- Reduction in Hb by 15g/l from best response or baseline (not felt to be associated with therapy)
- Increase in symptoms as noted by an increase of ≥50% in the MPN-SAF Total Symptom Score*
- Evidence of molecular clonal evolution

^{*} The use of the MPN-SAF Total Symptom Score within the International Consortium MDS/MPN Response Criteria is currently considered exploratory. Validation among patients within MDS/MPN is currently under way. (28)

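### Early stoppers are scored at stopping with criteria that include the MPN-SAF symptom score, but the stopping visit does not collect it

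*Protocol*

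**What the plan says.** Section 10.4.1 of the protocol defines overall response as clinical benefit or better under Appendix 3, read "at day 29 of the sixth or last cycle of tefinostat (whichever is the earliest"). A patient who stops early is thus scored at stopping.

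Appendix 3 uses the MPN-SAF Total Symptom Score twice. One route to clinical benefit is "improvement in symptoms as noted by a decrease of ≥50% in the MPN-SAF Total Symptom Score (only valid if baseline score>20"). A rise of at least 50% is one of five minor criteria of progression. A footnote calls this use exploratory, as does section 9.2. Neither 10.4.1 nor 8.3.6 takes it out of the endpoint, and 8.3.6 asks for prompt return of the form because "the MPN-SAF Total Symptom Score forms part of the International Consortium MDS/MPN Response Criteria".

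Section 8.5 covers patients who stop at times other than directly after the cycle 6 assessment, including those "withdrawn early (during cycles 1-5) due to unacceptable toxicity or clear disease progression". For them "the following additional assessments should be performed": clinical (8.5.1), laboratory (8.5.2), urinalysis (8.5.3) and bone marrow (8.5.4). No questionnaire is listed. In the section 8 schedule, quality of life is ticked at screening, day 85 and day 169, and the last column (loss of response, progression, intolerability) is blank. Section 9.2 agrees: "QoL will be measured at baseline (prior to the start of treatment) and following 3 and 6 four-week cycles of tefinostat therapy".

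**The concern.** The endpoint is read at a time when one of its inputs is not collected. The mismatch touches three things.

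- **Primary response.** A symptom improvement present at stopping cannot be shown.
- **Progression.** Section 8.5 provides the visit at which progression is documented, yet the symptom criterion cannot be scored there.
- **Quality of life.** Section 9.2 justifies measuring it by the systemic toxicity of non-selective HDAC inhibitors. Patients who stop for toxicity or progression bear most directly on that question, and no form is taken from them at stopping.

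A form not completed at the time cannot be recovered by any later analysis, so the matter belongs in the protocol.

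**Working it through.** **1. What the stopping visit supports.**

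| Appendix 3 input | Collected under 8.5? |
|---|---|
| Marrow blasts, cytogenetics, trephine | Yes, 8.5.4 |
| Blood counts | Yes, 8.5.2 |
| Transfusions | Yes, 8.5.1 |
| Spleen, liver, skin | Yes, 8.5.1 |
| MPN-SAF Total Symptom Score | No |

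**2. How old the latest score is at stopping.** Cycles last 28 days, so the end of cycle k falls on day 28k + 1. The cycle 4 form (8.2.10) and the end of cycle 6 form (8.3.6) each have a window of 7 days either side.

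| Stop at end of cycle | Day | Latest scheduled form | Gap in days |
|---|---|---|---|
| 1 | 29 | Baseline | 28 from start of treatment |
| 2 | 57 | Baseline | 56 from start of treatment |
| 3 | 85 | Day 85 | 0 |
| 4 | 113 | Day 85 | 28 |
| 5 | 141 | Day 85 | 56 |

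The baseline form is completed before treatment, so the first two gaps are minima. Among stops before the cycle 6 assessment, only one near day 85 has a current score. Section 8.4 has no MPN-SAF for patients continuing beyond cycle 6, so the gap recurs for those who stop later.

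**3. Effect on response.** Section 10.1 counts patients not known to have responded as non-responders. Every patient therefore has a status, and the error is downwards. It reaches a patient only if all of these hold: the stop is away from a scheduled form, the baseline score is above 20, the score has fallen by at least 50%, no other route to response is met, and there is no progression.

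**4. Effect on progression.** Progression needs 2 major, or 1 major and 2 minor, or 3 minor criteria. Adding one symptom item changes the call in two cases only:

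- 0 major and exactly 2 other minor criteria (2 + 1 = 3 minor);
- 1 major and exactly 1 other minor criterion (1 major, 1 + 1 = 2 minor).

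Section 10 has no rule for an unscored progression item. Because clinical benefit requires absence of progression, this gap works in the opposite direction to step 3: it can leave a response standing or a progression uncalled.

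**5. The plan's own design, then an illustration.** Inputs from section 10.1: 19 then 40 patients; continue with at least 3 responses and at most 6 toxicities; succeed with at least 7 responses and at most 12 toxicities. Taking response (probability p) and toxicity (probability q) as independent:

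- Efficacy: E(p) = sum over x = 3 to 19 of P(Bin(19, p) = x) × P(Bin(21, p) ≥ 7 − x). E(0.30) = 0.941; E(0.10) = 0.080.
- Toxicity: T(q) = sum over t = 0 to 6 of P(Bin(19, q) = t) × P(Bin(21, q) ≤ 12 − t). T(0.20) = 0.911; T(0.40) = 0.103.
- Joint power: 0.941 × 0.911 = 0.857, against 85% stated.
- Joint errors: 0.080 × 0.911 = 0.073 and 0.941 × 0.103 = 0.097, both within 10%.

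The documents give neither a stopping rate nor the share of responders who qualify by symptoms alone. Purely as an assumption, suppose 5% or 10% of true responses were lost:

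| Response rate | Efficacy power | Joint power |
|---|---|---|
| 0.30 | 0.941 | 0.857 |
| 0.30 × 0.95 = 0.285 | 0.919 | 0.837 |
| 0.30 × 0.90 = 0.27 | 0.891 | 0.812 |

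If 25% to 40% of responders stopped early (also an assumption), such losses would need between 0.05/0.40 = 12.5% and 0.10/0.25 = 40% of responders to qualify by symptoms alone. Nothing in the protocol supports or excludes that.

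**The case against.** The strongest reply is that little hangs on this score. The protocol twice calls its use exploratory, and the non-responder rule is conservative. Patients stopped for clear progression could not count as clinical benefit with or without the form. Section 10.4.1 speaks of a cumulative proportion, so the day 85 form may arguably count for those stopping in cycles 4 and 5. Under the illustrative losses above, efficacy power on its own stays above 85%. All of this stands, and it keeps the point small. It does not remove the mismatch: an exploratory item that is not excluded from a primary endpoint still counts, and the conservative default does not reach the progression item.

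A reader might infer that quality of life is known only for patients who stay on treatment. The documents do not support that. Every patient has a baseline form, those stopping in cycles 4 and 5 also have the day 85 form, and section 8.6 keeps patients who choose to stop treatment only under protocol assessment. What remains is under-representation. Those stopping for toxicity or progression follow 8.5, which has no form, and for patients withdrawn by the investigator 8.6 speaks of continuing safety assessments.

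**Conclusion.** The endpoint timing in 10.4.1, the criteria in Appendix 3 and the assessments in 8.5 do not fit together. For a patient who stops away from day 85 or day 169, the symptom response cannot be shown and is counted as absent, the symptom progression item cannot be scored, and no quality-of-life form is taken at stopping. The other main response and progression components remain scorable.

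Two larger conclusions are tempting. The first is that response or progression cannot be assessed at all in early stoppers; step 1 shows that only the symptom items are missing. The second is that the trial loses material power; that rests entirely on stopping and response-loss rates the documents do not give, and the table in step 5 is an illustration, not an estimate. The size of the effect cannot be derived from the protocol. This is a low-severity gap that is cheap to close.

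**What to change.** Add the MPN-SAF and the EQ-5D-5L to section 8.5 and tick them in the stopping column of the section 8 schedule, to be completed at the visit already required there. The cost is a small burden on patients: two self-completed questionnaires, with no extra visit or procedure. Sample size and decision boundaries do not change.

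If the sponsor does not want this, state in section 10.4 that the exploratory symptom items of Appendix 3 do not count towards primary response or progression. That removes the mismatch for the endpoints at no cost in data collection, but leaves quality of life as it is.

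A form at stopping adds information on stoppers. It does not stand in for their missing week 12 or week 24 values, and reports of quality of life at those times should say so.

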8.5.1 Clinical assessment

- Adverse events
- Concomitant medications
- Transfusion history
- Physical examination including liver and spleen size by palpation, lymph nodes, skin infiltration, gingival hypertrophy,
 cutaneous haemorrhages
- Vital signs and weight
- ECOG performance status (Appendix 6)

8.5.2 Laboratory assessments

- Full blood count to include haemoglobin, differential white cell count (including monocyte count and blast %), platelet count, MCV
- Biochemistry assessment: sodium, potassium, urea, creatinine (and eGFR), magnesium, calcium, phosphate, glucose,
 albumin, total protein, bilirubin, ALT/AST, alkaline phosphatase, LDH, uric acid

8.5.3 Urinalysis

• Using standard dipstick assessment (pH, protein, glucose, blood, ketones and leucocytes). This should be supplemented by formal quantification of any potentially-relevant abnormalities (eg. 24hr collection to quantify proteinuria).

8.5.4 Bone marrow assessment

 Bone marrow aspirate and trephine biopsy. Analysis of bone marrow aspirate to include morphological assessment (with differential count), local immunophenotypic (blast and monocytoid populations) and cytogenetic assessments.
 Local assessment of trephine histology.

8.6 Early withdrawal from the trial

Participants have the right to withdraw their consent from the study at any time for any reason. Should a patient decide to withdraw from the study, all efforts should be made to report the reason for withdrawal as thoroughly as possible. The investigator should ascertain from which aspects of the trial the patient wishes to withdraw and record the details in the appropriate part of the CRF (Form F). If a patient chooses to withdraw from treatment only the patient should continue to be assessed in accordance with the protocol. If a patient wishes to withdraw from the trial (i.e. including trial-specific assessments)

but is willing for further data to be supplied to CTR, then further routine follow-up data such as disease response status, survival and further treatment, will continue to be supplied by the investigator to CTR until 18 months after registration.

The local investigator also has the right to withdraw patients from the study treatment for a number of justifiable reasons including unacceptable toxicity (an adverse event or events that, in the judgment of the investigator, may cause severe or permanent harm or which rule out continuation of the study drug), unforeseen events which in the opinion of the investigator make further treatment inadvisable, serious violation of the study protocol (including persistent patient non-attendance and non-compliance) or for clinical reasons not related to the study treatment. Patients withdrawn by the investigator should continue to undergo safety assessments as per the trial schedule and to receive supportive care as per local policy.

9 DATA RECORDING

Data recording for this trial will be via a web-based system. This will be a secure encrypted system accessed via a user-specific password which will comply with Data Protection Act standards. The system will be accessed on:

https://medic.cardiff.ac.uk/monocle

A user password will be supplied to investigators on completion of the procedures described in section 6.1.

For centres that are unable to use the internet system, a patient record book will be made available to download from the trial website: http://medic.cardiff.ac.uk/monocle. This can also be sent to the consultant in charge of the patient's management upon request to CTR following trial entry.

The Case Report Form (CRF) will comprise a set of forms capturing details of eligibility, baseline characteristics, treatment and outcome details. Forms should be completed via either the web-based system or patient record book. The CRF must be completed, signed/dated and returned to the Trials Office by the investigator or by an authorised member of the patient's care team (as delegated on the Site Signature and Delegation Log) within specific time frames (see 9.1). For sites using the paper patient record book system, CRF entries should be made in ballpoint pen, in blue or black ink, and must be legible. Any errors should be crossed out with a single stroke, the correction inserted and the change initialled and dated.

Reported data should be consistent with the source data with any discrepancies being clearly explained. If information is not known, this should be clearly indicated on the form. All missing or ambiguous data will be queried. It is the responsibility of the investigator to ensure that the CRF has been completed correctly and that the data are accurate.

Over the course of the study, trial forms may be amended by CTR as appropriate. Whilst this will not constitute a protocol amendment, new versions of the form must be implemented by participating sites immediately upon receipt.

9.1 Data submission

Patient Eligibility Checklist / Registration (Form A) – should be completed at the time of patient registration and faxed to CTR ([name])

Baseline Assessment (Form B) – to be completed and submitted when all diagnostic data requested are available (but no later than 1 month after trial entry)

Course 1-6 Reports (Form C) – comprise data collected at day 1 and 15 visits during each cycle of tefinostat therapy. To be completed and submitted following each patient review.

End of Course 6 Efficacy Assessment (Form D) – to be completed and submitted when all data (including bone marrow reports) from the post cycle 6 efficacy assessment are available (within 14 days of the course 6 day 29 visit)

Continuing Therapy Reports (Form E) – for patients continuing beyond 6 cycles of tefinostat therapy. Comprise data collected at day 1 of each subsequent course of tefinostat. To be completed and submitted following patient review.

Withdrawal from Therapy (Form F) – to be completed following cessation of tefinostat therapy at time points other than immediately following the results of the post-cycle 6 efficacy assessment. This will include patients who stop therapy early due to toxicity or clear disease progression and also patients who lose their clinical response after continuing therapy beyond cycle 6. To be completed and submitted when all data from the end of study assessment (including bone marrow reports) are available (within 14 days of cessation of therapy).

12-month Follow-up (Form G) – to be completed and submitted 12 months after trial entry

18-month Follow-up (Form H) – to be completed and submitted 18 months after trial entry

9.2 Quality of Life data collection

CMML has a heterogeneous clinical phenotype with a variable spectrum of disease-related constitutional symptoms. Previous studies of non-selective HDAC inhibitors have been associated with generalised systemic toxicities including gastrointestinal effects, fatigue and insomnia with resulting impacts on quality of life (QoL). QoL is thus an additional important outcome measure in assessing impact of tefinostat treatment in this patient population. QoL will be measured at baseline (prior to the start of treatment) and following 3 and 6 four-week cycles of tefinostat therapy. The instruments used will be the EuroQoL EQ-5D-5L (Appendix 9) and the Myeloproliferative Neoplasm (MPN) Symptom Assessment Form (MPN-SAF) (Appendix 10). The EQ-5D is a standardised instrument for use as a measure of health outcome. The EQ-5D-5L descriptive system comprises five dimensions (mobility, self-care, usual activities, pain/discomfort, anxiety /depression). The

MPN-SAF is a 27-item validated tool which aims to assess the prevalence and severity of symptoms in patients with myeloproliferative neoplasms; its use in patients with myelodysplastic/myeloproliferative neoplasms including CMML is currently being validated. The MPN-SAF Total Symptom Score is currently included within the International Consortium MDS/MPN Response Criteria on an exploratory basis. (28, 29)

Patients should be able to undertake the assessment themselves, and the local trial team are asked to facilitate this and to return the responses promptly to CTR in the pre-paid envelopes.

